Title: COVID-19 Antibody and Reinfection Study

NCT number: 1589316-19

Revised: 8/1/2023

STUDY PROTOCOL AND STATISTICAL ANALYSIS PLAN

Goal:

The goal of this study is to establish a cohort of Kaiser Permanente Colorado (KPCO) members who have and have not had COVID-19 infection for serial antibody testing and PCR testing to:

- 1. Quantify antibody titers among participants over 9 months.
- 2. Determine the rates of recurrent infection among participants with prior COVID-19.
- 3. Examine association between antibody titer levels and risk of recurrent infection.

Description:

In this study, the Kaiser Permanente Colorado (KPCO) Institute for Health Research (IHR) will evaluate SARS-CoV-2 IgG antibody titers over time and correlate antibody titers with risk of recurrent infection. The investigators will identify KPCO members who have and have not had prior infection, enroll them into a cohort study, conduct serial surveys for new COVID-19 symptoms, and facilitate serial viral and antibody testing.

All laboratory testing procedures and clinical management of participants will be conducted by KPCO operations. The research team will identify participants, obtain consent, administer surveys to assess COVID-19 symptoms, and direct patients to the appropriate testing. Health outcomes on cohort participants will be tracked with survey data on symptoms, clinical and utilization data from the KPCO electronic health record (e.g., hospitalization), and laboratory data (e.g., viral test results).

This research-operations partnership strategy will generate data to better understand the implications of positive antibody titers to this novel pathogen.

Study Type: Observational

Study Model: Case-control nested in a prospective cohort study We will recruit participants into a prospective survey and testing cohort who had suspected or confirmed SARS-CoV-2 infection. We will also recruit randomly sampled patients of similar age, sex, and race/ethnicity with no evidence of previous SARS-CoV-2 infection.

Time Perspective: Prospective

Target Follow-up: 10 months

Study Population:

The study population will include individuals who are enrolled in KPCO's health plan. Individuals will be selected who have evidence of prior SARS CoV-2 infection and samples of the general KPCO membership of similar demographic characteristics who appear not to have had SARS CoV-2 infection.

Inclusion criterion:

- KPCO health plan members,
- 18 years and older,

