- Have a valid email address or phone number in the electronic health record.

Exclusion criterion:

- Opted out of research
- Participated in the pilot survey

Need a non-English language interpreter

HIPAA Privacy Rule Authorization and Informed Consent Process:

This study will ask for a waiver of HIPAA Privacy Rule Authorization to identify KPCO members who meet the inclusion and exclusion criteria (see above). It is not feasible to outreach this cohort without the waiver as the study will include large numbers.

This study will consent eligible members. Participants will be consenting to serial surveys, receipt of messaging about testing, and access to antibody testing. This study will consent patients electronically through the REDCap e-consenting process. They will also authorize study staff to track COVID-19 tests performed, testing results, risk factors for severe COVID-19 disease, and health outcomes. Participants' EHR data 24 months prior to enrollment into the study and up to 24 months after completing the study may be included the analyses.

Study Procedures:

After identifying and consenting members, we will administer a REDCap initial survey to inquire about current symptoms of COVID-19, prior symptoms of COVID-19, prior testing for COVID-19 (and results), prior or current quarantine or isolation, interest in getting tested, attitudes about testing, self-protective behaviors (e.g., social distancing, mask wearing), demographic information, employment category, and contact with patients or the public through their employment. We anticipate that the survey will take 10 minutes to complete. Follow-up surveys, conducted every 28 days, will inquire about new symptoms, new testing, current attitudes and current behaviors. Testing procedures and patient notification of viral and antibody results will be conducted by operations as part of routine medical care. Operations has notified us that antibody results will be made available on KP.org or the KP app. We will inform participants that they can obtain results there.

At the time of the baseline or follow-up surveys, based on the responses to questions about prior testing and symptoms on the surveys, individuals will be encouraged to seek viral or antibody testing.

Participants will receive a thank you email and a second email with instructions for obtaining viral and/or antibody testing, depending on their reported previous test(s) and result(s), and symptoms.

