Participants will be sent a follow-up REDCap survey every 28 days to track symptoms, testing and results, quarantine or isolation, attitudes about testing, and protective behaviors. After follow-up survey completion, participants will be provided the same instructions about testing, based on their responses, as for the baseline. We will conduct repeat antibody testing on individuals who test positive to assess for reductions in titer levels over time, and among individuals who have negative antibodies to see if they develop new evidence of infection. We will conduct repeat viral testing among individuals who report no symptoms in order to assess for new asymptomatic infections.

Upon completion of the study, all participants will be sent an "Exit Survey" and testing opportunity. After completing the survey, participants will be asked to complete a final nasal and antibody test as part of the study.

Protocol Revisions:

Within this cohort, we opted to conduct a nested case-control analysis to examine the association between antibody status and reinfection. A nested case-control analysis was selected to account for the complexities of pandemic changes over time and various vaccines used during the study period. In addition, antibody status (positive/negative) was used instead of titer levels, as titer ranges differed across test types.

Data Analysis:

We will describe the antibody testing results and rates of reinfection among the study participants. We will use a nested case-control study design to examine the association between antibody seronegativity and reinfection. Reinfection will be defined as a positive SARS-CoV-2 RNA test ≥ 90 days after the first positive RNA test. Participants with reinfections will be matched to controls without reinfections by age, sex, date of the first positive RNA test, date of the last serology test, and serology test type. Using conditional logistic regression, case patients will be compared to control patients on the last serologic test result, with adjustment for potential demographic and clinical confounders.

Privacy, Confidentiality and Data Security:

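### The last serology is not tied in time to the first infection or the reinfection, so the analysed exposure can predate seroconversion or be long out of date

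*Combined protocol and SAP*

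**What the plan says.** All references are to the combined protocol and SAP.

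- **Exposure (Data Analysis).** In a conditional logistic regression, "case patients will be compared to control patients on the last serologic test result". Under Protocol Revisions, "antibody status (positive/negative) was used instead of titer levels".
- **Outcome (Data Analysis).** "Reinfection will be defined as a positive SARS-CoV-2 RNA test ≥ 90 days after the first positive RNA test". This is the only interval rule in the analysis, and it governs the gap between RNA tests, not the timing of the serology.
- **Matching (Data Analysis).** Age and sex, plus "date of the first positive RNA test, date of the last serology test, and serology test type". Calipers and an index date for controls are not stated.
- **Who is enrolled (Study Model).** Members with past infection, and also a sample with no evidence of past infection.
- **When serology happens (Study Procedures; Risks and Benefits).** "Participants will be sent a follow-up REDCap survey every 28 days", with testing instructions after each survey. Antibody testing is repeated in positives "to assess for reductions in titer levels over time", and also in negatives. A final antibody test is requested at exit. Participants may decline any test.
- **How long outcomes can run.** "Target Follow-up: 10 months". The HIPAA and consent section adds that EHR data "up to 24 months after completing the study may be included the analyses".

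No sensitivity analysis on the timing of the serology is described.

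**The concern.** The third goal is to relate antibody to the risk of recurrent infection. For that, the serology should show the antibody response to the first infection and should still say something about status when the participant is re-exposed. The rule as written secures neither.

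**Too early.** Take a participant who enrols uninfected, tests antibody-negative in month 1, has a first positive RNA test in month 2, takes no further serology, and has a second positive RNA test in month 6. The two RNA tests are about four months apart, so this is a reinfection by the plan's definition. The participant enters the model as seronegative on a test taken before there was an infection to respond to. A test in the first days of that infection has the same fault.

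**Too old.** Testing is voluntary, so the gap from last serology to reinfection has no ceiling. The plan expects titers to fall, and it acknowledges vaccination during the study, so status can change in either direction after the test.

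Because the exposure is reduced to positive or negative, no titer remains in the model to signal waning. A weak or null odds ratio could not be told apart from the effect of mistimed tests.

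**Working it through.** The plan gives no odds ratio, seronegativity prevalence, reversion rate or sample size, so there is no figure to reproduce. Every rate below is an assumption used to show the mechanism. The true ratio for current seronegativity is set at 3.

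**1. Longest lag the documents permit.** From an exit test to the end of the EHR window is 24 months. For a participant whose only serology was at baseline it is 10 + 24 = 34 months.

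**2. Old tests, positives reverting only.** Let a share r of positives revert each month. After L months f = 1 − (1 − r)^L of those who tested positive are negative. Their average risk is (1 − f)·1 + f·3 = 1 + 2f, against 3 in those who tested negative. The expected ratio is 3/(1 + 2f). For r = 0.03 and L = 6, f = 1 − 0.97^6 = 0.167, and 3/1.334 = 2.25.

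| Lag (months) | r = 3% | r = 5% |
|---|---|---|
| 3 | 2.55 | 2.33 |
| 6 | 2.25 | 1.96 |
| 12 | 1.86 | 1.56 |
| 24 | 1.47 | 1.24 |

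Each row is a single lag, not a pooled estimate.

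**3. Old tests, change in both directions.** A simulation of 1:1 pairs used 20% seronegative at the test, 2% per month turning negative and 5% per month turning positive. A true odds ratio of 3 gave 2.82, 2.48, 2.05 and 1.62 at 1, 3, 6 and 10 months. At 24 months it fell below 1 (0.91), but that model lets each person change status only once, so I place no weight on the crossing.

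**4. Early tests, 1:1 discordant pairs.** In valid sets take p0 = 0.20 of controls seronegative. With an odds ratio of 3, p1 = 0.75/1.75 = 0.4286 in cases. The discordant-pair probabilities are p1(1 − p0) = 0.3429 and p0(1 − p1) = 0.1143. In early-test sets both members are negative with probability q, unrelated to outcome, so each discordant type has probability q(1 − q). With a share w of such sets,

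OR = [(1 − w)·0.3429 + w·q(1 − q)] / [(1 − w)·0.1143 + w·q(1 − q)].

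| q | w = 10% | w = 20% |
|---|---|---|
| 0.60 | 2.62 | 2.31 |
| 0.95 | 2.91 | 2.81 |

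For q = 0.95, w = 10%: (0.3086 + 0.00475)/(0.1029 + 0.00475) = 2.91. At q = 0.95 only 2 × 0.95 × 0.05 = 9.5% of the early-test pairs are discordant. The other 90.5% contribute nothing to the conditional likelihood. The loss is mainly of information.

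**5. Direction if the error is unequal.** Let Se be the chance that someone seronegative at exposure has a negative last test, and Sp the chance that someone seropositive has a positive one. With p0 = 0.20, Se = 0.90 throughout, and Sp = 0.85 in cases and 0.95 in controls, the observed seronegative proportions are 0.4714 and 0.22, giving an odds ratio of 3.16. With the Sp values exchanged they are 0.4143 and 0.30, giving 1.65. With Se = 0.90 and Sp = 0.95 in both groups it is 2.51.

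**The case against.** **Matching on the two dates already controls timing.** It makes the interval from infection to serology, and the calendar date, similar within a set. That supports the condition under which bias runs toward 1. It does not make a pre-infection or outdated test informative, and without calipers the degree of similarity is unknown.

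**Pre-infection tests do little harm.** This largely stands. Without vaccine antibody nearly all such tests are negative and the pairs drop out, as step 4 shows. The larger figures need about 60% negative, which fits only a mixed group of early-infection or vaccinated participants.

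**Two-year lags are unlikely.** This stands as to frequency. A reader might infer from the consent section that outcomes will be counted for 24 months after the study. It only permits use of EHR data. The target follow-up is 10 months, testing is prompted every 28 days, an exit test is requested, and later serology recorded in the EHR is not ruled out. Two years after an exit test is a permitted extreme, not an expected lag.

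**Last known serostatus is a legitimate predictor in itself.** This stands in part: the plan does not claim to measure status at the moment of exposure. Even so, a predictor of reinfection should postdate the first infection, and its meaning depends on its age. This objection does argue against confining the primary analysis to recent tests.

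**Conclusion.** The exposure rule as written admits tests that cannot describe the response to the first infection and tests that may no longer describe status at reinfection. The wording also does not confine the test to before the reinfection, and an exit test could fall after it.

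A reader might infer that the odds ratio must be biased toward 1. The documents do not support that as a certainty. It is the expected direction if error is similar in cases and controls and the test still carries some information. Unstated calipers and index dates, vaccination after the test, and behaviour change after a known result (which the plan itself anticipates) could each make the error unequal, and step 5 shows movement either way.

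On size, a true ratio of 3 becomes about 2.0 to 2.3 at a 6-month lag under the assumed rates. It becomes 2.91 or 2.81 when 10% or 20% of sets rest on pre-infection tests that are 95% negative, and 2.62 or 2.31 only if about 60% are negative. The actual size cannot be derived from the documents. The case for a change rests on the stated rule, which can misclassify exposure and is easily bounded.

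**What to change.** Amend the Data Analysis section as follows.

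1. Define the exposure as the last serology taken at least a pre-specified interval after the first positive RNA test, to allow for seroconversion, and before the case's reinfection date. Twenty-one days is an example; the investigators should justify the value.
2. Give each matched control the case's reinfection date as its index date, select the control's serology by the same rule, and match on the date of that eligible test.
3. Keep all sets that meet this rule in the primary analysis. A primary restriction to recent tests, such as 180 days, has no basis in the documents, and its cost in precision cannot be judged because no sample size or reinfection count is given.
4. Pre-specify a sensitivity analysis reporting the odds ratio by lag from serology to reinfection, for example up to 90, 91–180 and over 180 days.

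The cost is SAP wording, date filters on data already held, and one more table. Sets with no eligible test are lost; the number should be small but cannot be estimated from the documents. No new visit, test or consent is needed.

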The primary protection against a breach of privacy and confidentiality is in the structure of the data itself. The data extracted will include the minimum necessary to conduct the described research. Additional procedures will be in place to further protect members from a breach of confidentiality: 1) all data in study datasets will be identified only by a study-assigned unique ID number and will not include the medical record number of the subject; 2) a crosswalk table linking the study ID to a patient medical record number will be separately maintained on password-protected computers only accessible to study staff; 3) members of the study team have completed mandated training procedures and certifications, including special compliance training; new research team members (if any) will complete currently mandated training procedures and certifications prior to working on the study; and 4) the study protocol will be reviewed, approved, and monitored by the IRB. Furthermore, only aggregate data will be released in any public forum or publication.

Risks and Benefits:

This study includes surveys, information about COVID-19 viral and antibody testing, and prompts to get viral or antibody testing, including earlier access to antibody testing being offered at KPCO.

Participation in the study may give participants with symptoms messaging to get viral testing, which may be beneficial for their health and the health of their close contacts. For participants who do not have symptoms, they may learn they have been exposed to COVID-19 through antibody testing. The harms and benefits of obtaining this information are currently unknown. Participants are free to choose whether to get testing. Testing is not a requirement for participation. Testing procedures and medical management will be conducted by KPCO operations.

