The primary risk of this study is the potential for loss of confidentiality and privacy of a member, through a loss or inappropriate disclosure of study data. Providing information about a member's COVID-19 symptoms, testing and attitudes may make them feel uncomfortable. They can choose to only answer questions that they are comfortable answering. Additionally, there is also a small risk for discrimination among individuals who have a positive viral test, a negative or positive antibody test, and/or a change in employment location or duties if they disclose the results to their employer. Research staff will not disclose the results of any testing conducted among individual participants to their managers. There are some inherent physical risks in

testing from nasal swabs and blood draws. Finally, the tests KPCO makes available may be under Emergency Use Authorization and any results should be interpreted with caution. Although we will advise them not to, participants may change their behavior as a result of positive antibody test results and could put themselves or others at risk for infection if the test is inaccurate. Alternatively, participants may have an increase in anxiety if their test results are positive or negative. All of these risks described are considered minimal.

There are no known risks to investigators or staff. The benefits outweigh the minimal risks to participants.

Compensation to Participants:

No compensation will be provided to participants.

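### Reinfection is found only through voluntary RNA testing, and controls need no RNA test while at risk, so the odds ratio depends partly on whether testing differs by serostatus

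*Combined protocol and SAP*

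**What the plan says.** Outcome (Data Analysis): "Reinfection will be defined as a positive SARS-CoV-2 RNA test ≥ 90 days after the first positive RNA test". There is no other route to being a case.

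Controls (Data Analysis): "Participants with reinfections will be matched to controls without reinfections by age, sex". The other three matching factors are the date of first RNA positivity, the date of the latest serology and the type of assay. Adjustment is for confounders of a demographic or clinical kind, none of them listed. No sentence requires a control to have had an RNA test during the period at risk.

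Testing (Risks and Benefits): "Participants are free to choose whether to get testing" and "Testing is not a requirement for participation". Under Study Procedures, "based on the responses to questions about prior testing and symptoms on the surveys, individuals will be encouraged to seek viral or antibody testing". The emailed instructions vary, "depending on their reported previous test(s) and result(s), and symptoms".

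Knowledge of the exposure: Study Procedures states that "antibody results will be made available on KP.org or the KP app" and that participants will be told so. Risks and Benefits anticipates that "participants may change their behavior as a result of positive antibody test results", although they will be advised not to.

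Planned safeguards (Study Procedures): surveys every 28 days with testing instructions, further viral tests for participants without symptoms, and a request to all participants for a nasal swab and antibody test at exit.

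**The concern.** Cases and controls are not held to the same standard of evidence. A case has been tested and found positive. A control has only not been found positive, which covers both people who tested negative and people who were not tested while at risk.

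That would matter little if detection were unrelated to the exposure. Here the exposure is an antibody result that participants can look up, and the protocol itself expects some to act on a positive one. Serostatus could therefore influence whether a reinfection is detected as well as whether it occurs. The association between seronegativity and reinfection, which is the study's main analytical question, would then combine the two, and no step in the planned analysis separates them.

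**Working it through.** The documents give no sample size, reinfection rate, effect size or testing uptake, so there is no stated figure to reproduce. The check is algebraic, and every input below is an assumption.

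**Inputs**
- r1, r0: true reinfection risk in seronegative and seropositive participants; r0 is varied from 2% to 10%.
- d1, d0: probability that a reinfected person is RNA-tested in time to be detected.
- t1, t0: probability that a person who is not reinfected is RNA-tested in the window.
- RNA specificity is taken as 1. Within matched sets, sampling of controls is taken as unrelated to serostatus.

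**Planned analysis.** Everyone without a detected reinfection is a potential control, so

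observed OR = odds(r1 × d1) / odds(r0 × d0) ≈ true OR × d1/d0 when reinfection is uncommon.

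Worked case with r0 = r1 = 5%, d1 = 0.6, d0 = 0.5: detected risks are 0.030 and 0.025; odds are 0.030/0.970 = 0.0309 and 0.025/0.975 = 0.0256; OR = 1.21.

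| Uptake d1 v d0 | Ratio | Observed OR, true OR 1 | Observed OR, true OR 2 |
|---|---|---|---|
| 0.5 v 0.5 | 1.00 | 1.00 | 1.90 to 1.98 |
| 0.6 v 0.5 | 1.20 | 1.20 to 1.21 | 2.33 to 2.39 |
| 0.7 v 0.5 | 1.40 | 1.41 to 1.43 | 2.77 to 2.79 |
| 0.8 v 0.4 | 2.00 | 2.02 to 2.09 | 4.02 to 4.09 |
| 0.5 v 0.7 | 0.71 | 0.70 to 0.71 | 1.33 to 1.41 |
| 0.4 v 0.8 | 0.50 | 0.48 to 0.50 | 0.90 to 0.98 |

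Ranges run over r0 = 2% to 10%. Low uptake alone is nearly harmless (first row). Unequal uptake can create an association or hide one.

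**Controls restricted to people with a negative RNA test in the window.**

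observed OR = true OR × (d1/t1) / (d0/t0).

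- If d/t is the same in both serostatus groups, the true OR is recovered.
- If symptom-driven testing differs by serostatus, it is not. With d = 0.8 v 0.5 and t = 0.4 v 0.4 the factor is (0.8/0.4)/(0.5/0.4) = 1.60, so a true OR of 1 appears as 1.60 and a true OR of 2 as 3.20.
- The restriction can also introduce bias. With d = 0.7 v 0.7 and t = 0.5 v 0.4 the planned analysis is unbiased under the null, while the restricted one gives (0.7/0.5)/(0.7/0.4) = 0.80.

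**The case against.** There are four serious arguments on the other side.

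1. A reader might infer that any untested participant can be a control. The matching factors rule that out: a control has an earlier positive RNA test and a serology test of the same type at a similar date, which also partly aligns willingness to test. This stands as a limit on the problem. It does not show that the control remained free of reinfection afterwards.

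2. Asymptomatic viral testing and the exit swab are planned and are not described as depending on serostatus. They do reduce the problem. But they remain voluntary, they are not linked to control eligibility, and a negative swab at exit does not exclude a reinfection months earlier.

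3. A reader might infer that seropositive people will test less, so that seronegativity is bound to look harmful. The documents do not support this. No text ties viral-test prompts to the antibody result; the stated group for repeat viral testing is people without symptoms; and the anticipated behaviour change is not said to concern testing. Someone with symptoms may test whatever their serostatus. The mechanism is plausible but not established, and the bias can run in either direction.

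4. A reader might infer that recent test-negative controls should replace the planned ones, or that testing history is excluded from adjustment. The 1.60 and 0.80 results show that the restriction is a trade-off. The covariates are unlisted and utilization data are tracked (Description), so testing history is unspecified rather than excluded.

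**Conclusion.** The gap is real, and its effect is conditional. The plan lets undetected reinfections serve as controls and has no step that accounts for RNA testing in the period at risk. The odds ratio is distorted materially only if RNA testing of reinfected people differs by serostatus, and then by about the ratio of uptake, upward or downward. Under assumed inputs and no true effect, the results run from about 0.5 (0.4 v 0.8) to about 2.0 (0.8 v 0.4), with almost no bias at equal uptake. These figures illustrate sensitivity; they do not estimate the bias in this study. Because a modest imbalance could alter the main conclusion and the relevant data are already collected, the plan should include an explicit check. The documents do not support calling the planned analysis invalid or known to be biased in one direction.

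**What to change.** In Data Analysis, keep the planned matched analysis as primary and take each control's index date as the matched case's reinfection test date. Then add the following.

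- **Sensitivity analysis (a):** restrict controls to those with a negative RNA test at least 90 days after their first positive and within 28 days (one survey cycle) of the index date.
- **Sensitivity analysis (b):** keep all controls and adjust for the number of RNA tests between first infection and the index date. Exclude the case-defining test, since counting it would build the outcome into the covariate.
- **Reporting:** give RNA testing frequency by serostatus, split by symptomatic and routine testing. Describe the association as robust only if the primary analysis, (a) and (b) agree.

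The cost is SAP wording and analysis time. Consent already covers tracking of tests and results, and the 28-day surveys record symptoms and testing. Analysis (a) will have fewer eligible controls on top of five-factor matching; the documents give no cohort size or case count from which to estimate the loss. Neither analysis fully removes bias if symptom-driven testing differs by serostatus, so that limitation should be stated with the results.
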